4.5 Lack of Glycaemic Control, Rescue Therapy

The subjects will receive investigational product during the entire randomized study period. All subjects will also continue to be provided with open-label 1000 mg metformin tablets with instructions to continue open-label metformin treatment for the duration of the study.

Randomized subjects with a central laboratory FBG and HbA1c value meeting the criteria for lack of glycaemic control during treatment period may be eligible to receive open-label, prescribed rescue medication which may allow the subject to remain in the trial. In case of subjects who are taking glimepiride, increase of dose to 2mg should be preceded first for glycaemic control. If there is lack of glycaemic control with meeting the rescue criteria though increase of dose to 2mg, rescue medication should be prescribed.

Rescue therapy is open-label, any marketed sitagliptinin the dosage approved in Korea. Rescue medication should only be prescribed by investigator if required. No other rescue therapy is allowed. Treatment should be according local standards of care and approved prescribing guidance. All rescue decisions will be based on central laboratory fasting plasma glucose (FBG) and HbA1C.

Subjects who meet the following rescue criteria will be considered for rescue medication.

- Week 4 – 8 (excluding week 8) FBG >13.2 mmol/L (240 mg/dL)
- Week 8 – 24 (including week 24) FBG >11.1 mmol/L (200 mg/dL)
- Week 24 – Week 52 (including Week 52) HbA1c >8.0%

Randomized subjects who meet the repeated rescue criteria should be scheduled for a rescue visit. The rescue visit should take place as soon as possible but not later than 4 weeks after confirmation of repeated FBG and HbA1C. Rescue medication will be dispensed during rescue visit.

On rescue visit, following procedures will be conducted;

Physical exam contains measurement of weight, waist circumflex, pulse and blood pressure. BMI calculation will be conducted.

Subjects will be followed for laboratory assessment of efficacy and safety according to study plan FBG, HbA1c, CBC, AST, ALT, total bilirubin, BUN, creatinine, electrolytes, total cholesterol, triglyceride, HDL-cholesterol, urinalysis, hsCRP, adiponectin. All laboratory assessment will be done in central laboratory.

Diet and life-style counselling will be given to the subject.

Concomitant medications will be checked.

Subject diary will be reviewed for hypoglycaemic events.

New diary will be dispensed to the subjects.

All serious adverse events and adverse events will be collected. The subjects will continue their study medication (investigational product and open-label metformin) as before and continue the original schedule for the visits during the remainder of the treatment period. Rescued subjects with central laboratory HbA1c values greater than HbA1c values specified per protocol, for 13 weeks despite rescue medication will be discontinued (Discontinuation criteria no. 1) from the study and referred for additional antihyperglycaemic therapy.

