5.2.3 Hypoglycemic Event

The subject will be asked to always self-monitor symptoms suggestive of hypoglycaemia and to register any signs of hypoglycaemia in the supplied diary.

A hypoglycaemic event can be either

- An episode with symptoms and confirmed low glucose.
- An episode with low glucose.
- An episode with symptoms when glucose was not measured.

For the evaluation of hypoglycaemic events special attention will be given to hypoglycaemia as defined in accordance with CPMP guidance on clinical investigation of medicinal products in the treatment of diabetes mellitus, as described below.

- Major hypoglycaemic events, defined as symptomatic events requiring external assistance due to severe impairment in consciousness or behaviour, with a capillary or plasma glucose value <3.0 mmol/L (<54 mg/dL), and prompt recovery after glucose or glucagons administration.

- Minor hypoglycaemic event, defined as either a symptomatic event with a capillary or plasma glucose value <3.5 mmol/L (<63 mg/dL), and no need for external assistance, or an asymptomatic blood glucose measurement <3.5 mmol/L (<63 mg/dL).
- Events suggestive for hypoglycaemia, with symptoms that the subject experiences as hypoglycaemia and no confirmative measurement.

Data to be collected for each hypoglycaemic event:

- Date of start and stop and time of the day for start
- If symptoms are present or not and which symptoms
- If finger stick value obtained and the plasma glucose value
- Intervention needed for recovery, max intensity, action taken, causality and possible contributing factors
- Time of last drug administration
- Time of last meal

The subject's diary will be reviewed and data regarding hypoglycaemic events transcribed into the eCRFs at each clinical visit. A new diary for the next period will be handed over to the subject. If a major hypoglycaemic event occurs, or more than one minor event since last visit, the subject should contact the investigator. For recording of hypoglycaemic events/symptoms suggestive of hypoglycaemic events as AEs, see Section 6.3.

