7.2 Dose and treatment regimens

The investigational product, dapagliflozin or glimepiride, and additional drug, metformin 1000 mg will be taken orally.

Subjects to be allocated to the glimepiride group will start taking 1mg glimepiride at visit 2. At visit 3, 4, 5 and 6, glimepiride can be up titrated to 2 mg to maintain glycemic control at the discretion of the investigator after evaluation of glycaemic control in subjects. Glimepiride can be down titrated to mitigate recurrent hypoglycaemic events at the discretion of the investigator but 0mg is not allowed. If further hypoglycaemic events occur with meeting the discontinuation criteria after taking the 1mg glimepiride, subjects may be discontinued from investigational product.

Dapagliflozin or glimepiride should be taken once daily, in the morning, as instructed by the investigator, immediately before or together with a meal.

The investigational product should be taken at approximately the same time of the day during the study period. The metformin should be taken just before or together with a meal according to the investigator's instruction.

Subjects should be instructed to abstain from all food and beverages for 12 hours prior to each clinical visit; however, drinking water after midnight is allowed. In the morning prior to each visit, acceptable concomitant medications can be taken with water only.

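### The Week 4 to 8 rescue threshold pairs 13.2 mmol/L with 240 mg/dL, but 240 mg/dL is 13.3 mmol/L

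*Protocol*

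**What the plan says.** Protocol Section 4.5 lists three rescue criteria by study period. The first, for Week 4 up to but excluding Week 8, is "FBG >13.2 mmol/L (240 mg/dL". The second, for Week 8 to Week 24, is "FBG >11.1 mmol/L (200 mg/dL". The third uses HbA1c. Rescue decisions rest on central laboratory values.

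The same section limits what a single high value can do. It says "Subjects who meet the following rescue criteria will be considered for rescue medication" and then "Randomized subjects who meet the repeated rescue criteria should be scheduled for a rescue visit". For the glimepiride arm, "increase of dose to 2mg should be preceded first for glycaemic control". Section 7.2 adds that "Subjects to be allocated to the glimepiride group will start taking 1mg glimepiride at visit 2", with up-titration possible from Visit 3 onward.

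Two more glucose pairs appear in the hypoglycaemia definitions of Section 5.2.3: "<3.0 mmol/L (<54 mg/dL" for a major event and "<3.5 mmol/L (<63 mg/dL" for a minor one.

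SAP Section 3.1.3 refers to the rescue criteria without restating the thresholds. SAP Section 3.3 lists baseline fasting glucose in mg/dL. Neither document gives a conversion factor or names a governing unit.

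**The concern.** A threshold printed in two units should classify a patient the same way in either. This one does not. A repeated FBG above about 238 and up to 240 mg/dL meets the criterion in mmol/L and fails it in mg/dL. The line is an operative rule for starting sitagliptin in a 17-site trial, so it should have only one reading.

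The scheduled value in this window is the Week 4 sample at Visit 3. Glimepiride subjects are still on 1 mg at that point and go to 2 mg before rescue, so that value leads directly towards rescue only in the dapagliflozin arm.

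**Working it through.** **Inputs.** Four glucose pairs: 13.2/240 and 11.1/200 (Protocol 4.5), 3.0/54 and 3.5/63 (Protocol 5.2.3). Number randomized: 120, allocated 1:1 (Protocol synopsis and 1.4).

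**Step 1: factor implied by each pair** (mg/dL divided by mmol/L).

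| Pair | Implied factor |
|---|---|
| 240 / 13.2 | 18.18 |
| 200 / 11.1 | 18.02 |
| 54 / 3.0 | 18.00 |
| 63 / 3.5 | 18.00 |

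Three pairs agree on about 18. The Week 4 to 8 pair stands apart.

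**Step 2: try to reproduce the printed figure.** With a factor of 18, 240 / 18 = 13.33. With 18.016 (from the molar mass of glucose, a constant not given in the documents), 240 / 18.016 = 13.32. Both round to 13.3, not 13.2. In reverse, 13.2 × 18 = 237.6 mg/dL and 13.2 × 18.016 = 237.8 mg/dL. A coarse multiplier of 0.055 does return 13.2 (240 × 0.055 = 13.2), but it turns 200 mg/dL into 11.0, against the 11.1 printed for the next criterion.

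**Step 3: can rounding to one decimal explain it?**
- 13.2/240 needs a factor between 240 / 13.25 = 18.11 and 240 / 13.15 = 18.25.
- 11.1/200 needs a factor between 200 / 11.15 = 17.94 and 200 / 11.05 = 18.10.
- The ranges do not overlap.

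**Step 4: can truncation to one decimal explain it?**
- 13.2/240 needs a factor between 240 / 13.3 = 18.05 and 240 / 13.2 = 18.18.
- 11.1/200 needs a factor between 200 / 11.2 = 17.86 and 200 / 11.1 = 18.02.
- The ranges do not overlap.

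No single factor yields both FBG rescue criteria under either convention.

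**Step 5: size of the gap.** 240 − 237.6 = 2.4 mg/dL, and 2.4 / 240 = 1%.

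**Step 6: how many subjects might fall in it.** The dapagliflozin arm has about 120 / 2 = 60 subjects. The documents give no FBG distribution, so the means and SDs below are assumptions. Expected number = 60 × normal probability of a value between 237.6 and 240 mg/dL.

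| Assumed Week 4 mean, SD (mg/dL) | Share in gap | Expected number of 60 |
|---|---|---|
| 135, 30 | 0.00805% | 0.005 |
| 150, 40 | 0.204% | 0.12 |
| 170, 45 | 0.661% | 0.40 |
| 180, 50 | 0.959% | 0.58 |

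These counts are before the requirement for a repeat value and assume that every subject is sampled within the window.

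**The case against.** The best case on the other side accepts the arithmetic and argues that nothing follows from it.

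- **No automatic consequence.** The criterion must be repeated, and the investigator prescribes rescue only if required. The primary ANCOVA contains only treatment and baseline (SAP 3.7.2), and rescue-visit results enter only the LOCF for the HbA1c response (SAP 3.1.3 and 3.1.4). All of this stands, and it is why the point is minor.
- **Sites may never convert.** If the central laboratory reports in mg/dL, as the SAP's unit suggests, staff simply read 240. That is plausible, but neither document states the laboratory's reporting unit.
- **The gap may be narrower than 2.4 mg/dL.** If results come in mmol/L to one decimal, exceeding 13.2 means a reported 13.3 or more. At a factor of 18, 238 mg/dL is 13.22 and is reported as 13.2, so among whole mg/dL values only 239 and 240 are classified differently. This is correct, and the width does depend on the reporting convention. The mismatch remains.
- **Some subjects may have no scheduled value in the window.** Visit 3 may fall up to 7 days early, before Week 4 begins. This too is correct, and it lowers the expected counts further.
- **The correction may come too late.** The synopsis expects the last subject to complete in 4Q 2017, and the SAP edition is dated 08 February 2018. If treatment has ended, a protocol change would alter no decision.

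These points bear on size. None of them makes the two figures equal.

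**Conclusion.** The printed pair is wrong. At the protocol's own conversion, 240 mg/dL is 13.3 mmol/L, and no common rounding or truncation rule reconciles 13.2/240 with 11.1/200. That conclusion rests on the protocol's figures alone.

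The consequence is very small. The expected number of dapagliflozin subjects between the two values is below one in every scenario tried, from 0.005 to 0.58. Those scenarios are illustrative assumptions, not a bound. Nothing here affects the primary analysis model, the type I error or the power. The arm asymmetry is a fair reading of the titration rules, but an effect this small gives no ground for alleging bias. This is a desirable correction to an operative threshold and no more.

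**What to change.** Ask the sponsor which figure was intended. The SAP's use of mg/dL for fasting glucose points to 240 mg/dL, in which case the Section 4.5 criterion should read `FBG >13.3 mmol/L (240 mg/dL)`. If 13.2 mmol/L was the intended cut-off, it should read `FBG >13.2 mmol/L (238 mg/dL)`.

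The cost is one number in one line, with no change to the SAP or the data. It can go into the next protocol version. If the sponsor judges the change substantial, Protocol Section 10.5 requires an amendment with IRB approval. If no further version will be issued, a sentence in the study report stating which unit was applied would settle the matter.

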5. STUDY ASSESSMENTS

Web Based Data Capture system will be used for data collection and query handling. The investigator will ensure that data are recorded on the electronic Case Report Forms as specified in the study protocol and in accordance with the instructions provided. The investigator ensures the accuracy, completeness, and timeliness of the data recorded and of the provision of answers to data queries according to the Clinical Study Agreement.

5.1 Efficacy assessments

5.1.1 Dual Energy X-Ray Absorptiometry (DXA)

Whole-body DXA will be used for the estimation of body composition. The relative attenuation of two different x-ray energies by body tissues produces a three-component model comprising total fat mass.

The DXA scans should be performed to evaluate the total body fat and lean mass according to the manufacturer's manual for the DXA equipment, including the instructions for positioning, scan mode and specific information regarding the regions of interest.

Local evaluation will be done and whole-body DXA machines regardless of any manufacturer can be used in study sites. Standardization and level pre-check will be conducted prior to the start of the study.

5.1.2 CT

The CT scan will be performed using standard clinical scanners to evaluate abdominal VAT and SAT volume.

Subcutaneous and visceral fat will be measured using a Multi-detector CT scan. The scans will be done at 100-120 kV, effective mAs. All the patients will be scanned in the craniocaudal or caudocranial direction while they are lying in the supine position with their arms above their head and legs elevated with a cushion. We will acquire five 5-mm thickness slices at the level of the umbilicus with 25mm and 50mm increment and analyzed for a cross-sectional area of adipose tissue, which was expressed in centimeters squared. Areas will be calculated by multiplying the number of pixels of a given tissue type by the pixel number (pixel density). A post processing software (TeraRecon; TeraRecon, Inc., Foster City, CA) will be used for VAT and SAT volume measurement. The CT attenuation of fat will be defined as ranging from -190 to -30 HU. The parameters studied will include visceral fat amount (V) (cm²), subcutaneous fat amount (S) (cm²), V/V+S (%), and belly outer circumference (cm). Visceral fat was distinguished from subcutaneous abdominal fat by tracing along the fascial plane defining the internal abdominal wall. CT scan will not be conducted to the subjects who have contraindications to this procedure.

5.1.3 Height, Weight and Waist Circumference

Height will be measured without shoes (in cm), weight will be measured with light clothes and without shoes (in kg). All readings should be recorded as accurately as possible and the same scale should be used for all assessments for a given subject.

The waist circumference (in cm) will be measured in the morning before breakfast. The waist circumference is measured midway between the lowest rib and the iliac crest. (WHO Report 1987). Measurement should be made at the end of a normal expiration in a standing position and with measuring tape used in the study site.

5.1.4 BMI

BMI will be computed by AstraZeneca.

$BMI = \text{weight}/\text{height}^2$ (where weight is measured in kg, and height in metres).

BMI will be calculated using the height measured at enrolment.

5.1.5 Pulse and Blood Pressure

One pulse measurement will be taken after the subject has been sitting and resting for at least 5 minutes. Blood pressure will be measured using a standardized cuff adapted to the size of the subject's arm while the subjects remain comfortably in a seated position with the arms raised to the level of the heart and in a supported position.

5.1.6 Physical Examination

A physical examination will include an assessment of the following: general appearance, respiratory, cardiovascular, abdomen, head and neck including head, ears, eyes, nose and throat). The examination at Visit 1 is regarded as baseline data and new findings at the following physical examinations are recorded as change from baseline. Physical examination will also be performed in case of discontinuation of IP.

5.1.7 Laboratory Efficacy Assessments

5.1.7.1 HbA1c

Blood sample for laboratory measurement of HbA1c will be performed at Visit 1, 4, 5, 6, 7 and rescue visit. Laboratory assessments will be done at central laboratory.

5.1.7.2 Fasting Blood Glucose (FBG)

Blood sample for laboratory measurement of the concentration of glucose in the plasma after the patient has not eaten for 12 hours will be performed at Visit 1, 3, 4, 5, 6, 7 and rescue visit. Laboratory assessments will be done at central laboratory.

5.1.7.3 hsCRP and Adiponectin

Blood sample for laboratory measurement of hsCRP and adiponectin in the plasma after the patient has not eaten for 12 hours will be performed at Visit 1, 7 and rescue visit. Assessment will be done in central lab.

5.2 Safety assessments

5.2.1 Laboratory safety assessments

Blood sample for laboratory measurement will be performed at central laboratory.

Table 2 Laboratory Safety Variables

Haematology/Haemostasis (whole blood)	Clinical Chemistry (serum or plasma)
B-Haemoglobin (Hb)	S/P-Creatinine
B-Leukocyte count	S/P-Bilirubin, total
B-Leukocyte differential count (absolute count)	S/P-Alkaline phosphatase (ALP)
B-Platelet count	S/P-Aspartate transaminase (AST)
	S/P-Alanine transaminase (ALT)
Urinalysis (dipstick)	S/P-Albumin
U-Hb/Erythrocytes/Blood	S/P-Potassium
U-Protein/Albumin	S/P-Calcium, total
U-Glucose	S/P-Sodium
	S/P-Creatine kinase (CK)

5.2.2 12-Lead ECG

A 12-lead ECG will be taken (supine position, standard ECG with a recommended paper speed of 50 mm/second covering at least 6 sequential beats) after the subject has been lying down resting for at least 5 minutes. The ECG will be evaluated by the investigator and entered as “Normal” or “Abnormal” in the eCRF. If the ECG is evaluated as “Abnormal” the abnormality should be further specified.

5.2.3 Hypoglycemic Event

The subject will be asked to always self-monitor symptoms suggestive of hypoglycaemia and to register any signs of hypoglycaemia in the supplied diary.

A hypoglycaemic event can be either

- An episode with symptoms and confirmed low glucose.
- An episode with low glucose.
- An episode with symptoms when glucose was not measured.

For the evaluation of hypoglycaemic events special attention will be given to hypoglycaemia as defined in accordance with CPMP guidance on clinical investigation of medicinal products in the treatment of diabetes mellitus, as described below.

- Major hypoglycaemic events, defined as symptomatic events requiring external assistance due to severe impairment in consciousness or behaviour, with a capillary or plasma glucose value <3.0 mmol/L (<54 mg/dL), and prompt recovery after glucose or glucagons administration.

- Minor hypoglycaemic event, defined as either a symptomatic event with a capillary or plasma glucose value <3.5 mmol/L (<63 mg/dL), and no need for external assistance, or an asymptomatic blood glucose measurement <3.5 mmol/L (<63 mg/dL).
- Events suggestive for hypoglycaemia, with symptoms that the subject experiences as hypoglycaemia and no confirmative measurement.

Data to be collected for each hypoglycaemic event:

- Date of start and stop and time of the day for start
- If symptoms are present or not and which symptoms
- If finger stick value obtained and the plasma glucose value
- Intervention needed for recovery, max intensity, action taken, causality and possible contributing factors
- Time of last drug administration
- Time of last meal

The subject's diary will be reviewed and data regarding hypoglycaemic events transcribed into the eCRFs at each clinical visit. A new diary for the next period will be handed over to the subject. If a major hypoglycaemic event occurs, or more than one minor event since last visit, the subject should contact the investigator. For recording of hypoglycaemic events/symptoms suggestive of hypoglycaemic events as AEs, see Section 6.3.

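### A single hypoglycaemic event that needed another person's help, with glucose 3.0 to <3.5 mmol/L or unmeasured, triggers neither the contact rule in 5.2.3 nor the one-event stop in 4.3

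*Protocol*

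**What the plan says.** Protocol section 5.2.3 sets out three classes, which it says follow CPMP guidance.

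- **Major:** a symptomatic event in which someone else had to help because consciousness or behaviour was severely impaired, "with a capillary or plasma glucose value <3.0 mmol/L (<54 mg/dL), and prompt recovery after glucose or glucagons administration".
- **Minor:** either "a symptomatic event with a capillary or plasma glucose value <3.5 mmol/L (<63 mg/dL), and no need for external assistance", or a reading below 3.5 mmol/L without symptoms.
- **Suggestive:** "Events suggestive for hypoglycaemia, with symptoms that the subject experiences as hypoglycaemia and no confirmative measurement".

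The same section tells the subject when to call: "If a major hypoglycaemic event occurs, or more than one minor event since last visit, the subject should contact the investigator". It expects that some events will have no reading. One of its listed forms of hypoglycaemic event is "An episode with symptoms when glucose was not measured", and the data items include "If finger stick value obtained and the plasma glucose value". The routine route to the site is the diary: "diary will be reviewed and data regarding hypoglycaemic events transcribed into the eCRFs at each clinical visit".

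Two stopping provisions use these classes. Section 4.3 makes discontinuation mandatory after one major event or recurring minor events. Section 3.9 names the same threshold but is permissive. Both sections explain recurring minor events as any recurrent non-major hypoglycaemia, in the investigator's judgement. The contact rule carries no such explanation.

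The analyses (protocol 8.5.2, SAP 3.9.1.7) count subjects with at least one hypoglycaemic event of any kind. The SAP does not use the major and minor classes.

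**The concern.** The definitions leave a hole where severity is high. Needing help takes a symptomatic event out of the minor class, but it enters the major class only with a measured value below 3.0 mmol/L. A subject too impaired to self-test may well have no reading, and under these rules a missing reading lowers the class of the event.

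The contact rule is the only instruction in the protocol that asks the subject to bring hypoglycaemia to the investigator between visits. If it misses an assisted event, the later safeguards may start late, because each needs the site to know of the event. Section 1.1 names hypoglycaemia as a frequent side effect of sulfonylureas, and section 7.2 allows glimepiride to be raised to 2 mg at Visits 3 to 6.

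**Working it through.** **Inputs.** Class definitions and contact rule: 5.2.3. Mandatory stop: 4.3. Permissive criterion: 3.9. Visit weeks 0, 4, 12, 24, 36 and 52: Table 1. The thresholds are given in both units, 3.0 mmol/L (54 mg/dL) and 3.5 mmol/L (63 mg/dL). With an assumed factor of 18.016 they agree: 3.0 × 18.016 = 54.0 and 3.5 × 18.016 = 63.1.

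**Step 1: classify symptomatic events.** Assistance (no, yes) × glucose (three states) gives 2 × 3 = 6 cells. For the assisted row, severe impairment and prompt recovery are taken as met, which favours the plan.

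| | <3.0 mmol/L | 3.0 to <3.5 mmol/L | Not measured |
|---|---|---|---|
| No assistance | minor | minor | suggestive |
| Assistance | major | no class | suggestive |

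The middle assisted cell is not major (glucose is not below 3.0), not minor (help was needed) and not suggestive (a measurement exists). The unclassed band is 54 to <63 mg/dL.

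**Step 2: apply the rules to one assisted event.**

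| Rule | <3.0 mmol/L | 3.0 to <3.5 mmol/L | Not measured | Fires in |
|---|---|---|---|---|
| Contact (5.2.3) | yes | no | no | 1 of 3 |
| Mandatory one-event stop (4.3) | yes | no | no | 1 of 3 |
| One-major-event criterion (3.9, permissive) | yes | no | no | 1 of 3 |

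Reading the middle cell as minor would not help: a single event is neither more than one nor recurring.

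**Step 3: relax the favourable assumption.** An assisted event below 3.0 mmol/L without severe impairment, or without prompt recovery, also fails the major definition. It is not minor, because help was needed. The gap is therefore somewhat wider than the tables show.

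**Step 4: compare what the contact rule does catch.** Two asymptomatic readings of 3.4 mmol/L are 2 minor events; 2 > 1, so contact is prompted. Two assisted events at 3.2 mmol/L are 0 major and 0 minor under 5.2.3, so contact is not prompted. Once known to the site, those two could fall under the recurrence wording in 3.9 and 4.3.

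**Step 5: bound the delay.** The gaps between scheduled visits are 4 − 0 = 4, 12 − 4 = 8, 24 − 12 = 12, 36 − 24 = 12 and 52 − 36 = 16 weeks (sum 52). If nobody contacts the site, these are the longest nominal waits until diary review. They are not expected delays. The 16-week gap follows Visit 6, where up-titration to 2 mg is still allowed.

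**The case against.** The strongest reply accepts the literal reading and disputes its weight.

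- **The stop in 4.3.** Asking for biochemical confirmation before compulsory removal after one episode is defensible, and 3.9 already lets the investigator stop treatment for an adverse event. This stands: 4.3 need not change, and the remedy lies in the contact rule.
- **The source of the definitions.** They are attributed to CPMP guidance, which is not available here. This also stands as a reason to leave them alone. It does not justify using classes that depend on a glucose value as the only trigger for a subject to call.
- **Other safeguards.** Section 7.1 allows glimepiride to be down-titrated at any time, 6.2 allows an event to be judged serious, and 6.3.5 accepts spontaneous reports from patients or carers. The contact rule forbids no call. All true, but these are routes rather than prompts, and the first two need the site to know. Even the 24-hour reporting clock in 6.4 starts when site staff become aware.
- **Material not seen.** The diary and consent form are not in the documents, Table 1 is incomplete in the available copy, and 6.3.5 mentions a follow-up telephone contact. An instruction or interim call that closes the gap in practice cannot be excluded. This limits what can be said about consequences, not about the protocol text.
- **The comparisons.** Two asymptomatic readings against one assisted event is not like for like, and one asymptomatic reading triggers nothing either. Reading the recurrence wording of 3.9 and 4.3 into 5.2.3 would also bring two assisted events within the contact rule. That is a fair alternative reading, but it leaves the single event uncovered.
- **Practical size.** Glimepiride is capped at 2 mg, section 1.3 describes a low hypoglycaemia risk with dapagliflozin, and no frequency can be shown. This is why the point is a recommended correction and not a condition for the trial to proceed.

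**Conclusion.** The concern holds. As written, one symptomatic event that needed another person's help triggers neither the contact rule nor the mandatory one-event stop when glucose was 3.0 to <3.5 mmol/L or was not measured. Each rule fires in 1 of 3 assisted cells even when severe impairment and prompt recovery are granted. That count describes the definitions and says nothing about how often such events occur.

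The event is not lost. It is still a hypoglycaemic event, should appear in the diary, and enters the planned incidence summary and Fisher's exact test, so no analysis is affected. The cost is in timeliness: the investigator's decision on dose or continuation may wait for the next visit. This practical consequence assumes that the diary, consent form and any interim calls give no wider instruction to contact the site. The reading of the definitions needs no such assumption.

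**What to change.** Add to the contact rule in 5.2.3, and to the diary if it does not already say so: *The subject or a relative should also contact the investigator after any event that needed another person's help, whatever the glucose value and whether or not it was measured.*

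The investigator then reviews that single event against 3.9 and 4.3 and decides whether to continue, reduce glimepiride from 2 to 1 mg (0 mg is not allowed), or stop investigational product. The class definitions and the wording of 4.3 stay as they are.

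No further data item is needed, because 5.2.3 already collects "Intervention needed for recovery, max intensity, action taken, causality and possible contributing factors". The cost is a one-sentence amendment with IRB approval, and national regulatory approval if applicable, under 10.5. Add a few more unscheduled contacts and, if the present diary lacks the instruction, a revised diary for 17 sites. No planned analysis changes.
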